### ***F2 Interim Monitoring and Early Stopping***

The principal investigator will be responsible for routine monitoring of the trial's progress. This monitoring includes scheduled biweekly meetings with study staff and review of written documentation. Data that are reviewed at these meetings include the number and type of participants enrolled, the number and reasons for exclusions from enrollment, the number of participants treated and the stage of intervention, a summary and an individual review of any unanticipated health events, and outcome data. In addition, any unanticipated health events that raise concerns (e.g., allergic reaction, symptoms suggestive of nicotine toxicity) will be immediately reported to the study physicians (PI psychiatrist and Safety Consultants cardiologist and internist).

To facilitate participant safety, study participants must meet study inclusion and exclusion criteria. Once enrolled, follow-up protocols will assess the presence of medication side effects and unanticipated health events at all study visits and follow-up contacts. We will recommend dosage/use alterations as per good clinical practice if the patient experiences symptoms of nicotine toxicity or other troublesome side effects. We will refer patients to the study physician as needed. If participants are smoking regularly and heavily ( $\geq 5$  cigs daily), we will tell them to discontinue taking the study medication.

Should either excessive risk to study participants and/or lack of measurable benefit to study participants be determined, the study will be stopped and all participants notified in a manner appropriate to the nature of the risk and/or lack of benefit.

There is no plan of interim analyses of the primary hypothesis.

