#### 2.a Inclusion Criteria

Inclusion:

- 1) Adult (>=21 years of age), seeking treatment for smoking cessation.
- 2) Able to speak English,
- 3) Active smoking (Cigarettes Per Day (CPD) >=5) and exhaled CO >=8 ppm
- 4) Agree to participate in this randomized smoking cessation trial with follow up assessments up to 12 months, and

---

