## **2.g When and How to Withdraw Subjects**

We are conducting this research with strong safety measures in place (close monitoring and screening) to gather the needed data without imposing unacceptable risks. The participants will remain under the care of their own physician(s) throughout the study. To facilitate safety, participants who are not medically appropriate to take combination NRT or varenicline will not be included in the study (see exclusion criteria). Once enrolled, follow-up protocols will assess the presence of medication side effects and unanticipated health events at all study visits and follow-up contacts. We will recommend dosage/use alternations as per good clinical practice if the patient experiences symptoms of nicotine toxicity or other troublesome side effects once they begin medication treatment. We will refer patients to the study physician as needed.

Participants' medications will be continued if they have relapsed to smoking regularly. Subjects with symptoms of nicotine toxicity (including diarrhea, abdominal pain, vomiting, dizziness, and headache) reported at any research contact will be told to discontinue their medication immediately until they have a chance to discuss their symptoms with the study physician ([name]) or their primary care doctor, who will decide upon a course of action based upon the patient's status and risk (e.g., a dose reduction or medication discontinuation). Emergency care will be administered as needed. If the only severe symptom is sleep disturbance, subjects will be instructed to remove the patch at night, but otherwise keep receiving treatment according to the protocol. Should either excessive risk to study participants and/or lack of measurable benefit to study participants be determined, the study will be stopped and all participants notified in a manner appropriate to the nature of the risk and/or lack of benefit.

Any patient who reports discomfort as a result of completing the assessment of depression and anxiety will be reminded that the evaluation is discretionary, that it will be discontinued if the patient wishes, and that doing so will not affect the patient's medical care. The experienced psychiatrist investigator will be on call in case a patient has an adverse reaction to a screening or outcome evaluation. We have administered these tests to over 2,500 patients without a single subject reporting more than mild, transient emotional distress.

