### **3.b Treatment Regimen**

During the baseline visit (visit 1), all participants will be randomized at 1:1:1 to 1) one arm of combination nicotine and smoking cessation counseling, or 2) varenicline and smoking cessation counseling, and 3) another arm of placebo and smoking cessation counseling at no cost to participants. Participants will receive enough patches to last 12 weeks. The duration of medication treatment is 12 weeks (standard for participants who smoke >9 cigs/day=8 weeks of 21mg, 2 weeks of 14mg, and 2 weeks of 7mg nicotine patches; standard for participants who smoke 5-9 cigs/day=8 weeks of 14mg and 4 weeks of 7mg;).

**Nicotine Lozenge:** The 4 mg dosage is recommended for patients who take their first cigarette within 30 minutes of waking and the 2mg dosage is recommended for patients who take their first cigarette more than 30 minutes after waking. Participants will begin taking lozenges a week before abstinence to replace some cigarettes. Participants will then take 1 lozenge every 1-2 hours for 6 weeks, then 1 lozenge every 2-4 hours for 3 weeks, and 1 lozenge for every 4-8 hours for 3 weeks. Participants will be encouraged to take a minimum of 4 pieces/day unless this amount produces adverse effects.

**Varenicline:** Varenicline will be initiated with a titration for 7 days before the quit date. Before the quit date, participants will take one 0.5mg tablet daily for 3 days, then two 0.5mg tablets for 4 days (one in the morning and one in the evening). After the quit date (day 8), participants will take 1mg tablet in the morning and in the evening.

**Placebo:** 50% of participants assigned to the placebo group will receive placebo patch/lozenge, and 50% will receive the placebo pill as a control for the two active medication arms.

All participants will be given complete instructions on proper medication use, and will be urged to contact his/her physician and a study hotline number immediately in case of listed symptoms of nicotine toxicity or side effects. Dose changes or discontinuation of NRT may be recommended; all changes will be addressed in analyses of adherence outcomes.

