#### **4.b Medical Monitoring**

The principal investigator will be responsible for routine monitoring of the trial's progress. This monitoring includes scheduled biweekly meetings with study staff and review of written documentation. Data that are reviewed at these meetings include the number and type of participants enrolled, the number and reasons for exclusions from enrollment, the number of participants treated and the stage of intervention, a summary and an individual review of any unanticipated health events, and outcome data. In addition, any unanticipated health events that raise concerns (e.g., allergic reaction, symptoms suggestive of nicotine toxicity) will be immediately reported to the study physicians (PI psychiatrist).

To facilitate participant safety, study participants must meet study inclusion and exclusion criteria. Once enrolled, follow-up protocols will assess the presence of medication side effects and unanticipated health events at all study visits and follow-up contacts. We will recommend dosage/use alterations as per good clinical practice if the patient experiences symptoms of nicotine toxicity or other troublesome side effects. We will refer patients to the study physician as needed.

If participants are smoking regularly, we will tell them to continue taking the study medication and set another quit date as soon as possible. Should either excessive risk to study participants and/or lack of measurable benefit to study participants be determined, the study will be stopped and all participants notified in a manner appropriate to the nature of the risk and/or lack of benefit.

---

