## **H Study Monitoring, Auditing, and Inspecting**

### **H1 Study Data Safety and Monitoring Plan**

This study has a Data Safety and Monitoring Plan (DSMP), and a Data and Safety Monitoring Board (DSMB). The Individual Patient Safety Committee (IPSC) will include three of the study's key personnel: [name]., M.P.H., Sc.D., a psychiatrist; [name]., a psychologist, [name]., a psychiatrist; The IPSC will review monthly reports on all participants. The IPSC will be blinded to the patient's group assignment.

The principal investigator will be responsible for routine monitoring of the trial's progress. This monitoring includes scheduled biweekly meetings with study staff and review of written documentation. Data that are reviewed at these meetings include the number and type of participants enrolled, the number and reasons for exclusions from enrollment, the number of participants treated and the stage of intervention, a summary and an individual review of any unanticipated health events, and outcome data. In addition, any unanticipated health events that raise concerns (e.g., allergic reaction, symptoms suggestive of nicotine toxicity) will be immediately reported to the study physicians (PI psychiatrist and Safety Consultants cardiologist and internist).

To facilitate participant safety, study participants must meet study inclusion and exclusion criteria. Once enrolled, follow-up protocols will assess the presence of medication side effects and unanticipated health events at all study visits and follow-up contacts. We will recommend dosage/use alterations as per good clinical practice if the patient experiences symptoms of nicotine toxicity or other troublesome side effects. We will refer patients to the study physician as needed. If participants are smoking regularly, we will tell them to continue taking the study medication and set another quit date as soon as possible. Should either excessive risk to study participants and/or lack of measurable benefit to study participants be determined, the study will

---

be stopped and all participants notified in a manner appropriate to the nature of the risk and/or lack of benefit.

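### Section F2 tells participants smoking 5 or more cigarettes a day to stop study medication; sections 2.g, 4.b and H1 tell them to keep taking it

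*Combined protocol and SAP*

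**What the plan says.** Four sections of the protocol say what happens to study medication when a participant is smoking during treatment.

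- **F2 (Interim Monitoring and Early Stopping):** for participants smoking regularly and heavily, defined as at least 5 cigarettes a day, "we will tell them to discontinue taking the study medication".
- **2.g (When and How to Withdraw Subjects):** participants' "medications will be continued if they have relapsed to smoking regularly". The only stop rule in this section is for symptoms of nicotine toxicity.
- **4.b (Medical Monitoring):** "If participants are smoking regularly, we will tell them to continue taking the study medication and set another quit date as soon as possible".
- **H1 (Data Safety and Monitoring Plan):** the same instruction, "we will tell them to continue taking the study medication and set another quit date as soon as possible".

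Three other provisions bear on the point. The inclusion criteria in 2.a require "Active smoking (Cigarettes Per Day (CPD) >=5) and exhaled CO >=8 ppm". Section 3.b states "The duration of medication treatment is 12 weeks". It also says "Dose changes or discontinuation of NRT may be recommended; all changes will be addressed in analyses of adherence outcomes".

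**The concern.** A participant who reports 10 cigarettes a day at the week 2 call is to be told to stop under F2 and to continue under the other three sections. Nothing in the document says which rule prevails.

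The primary outcome (E5) is CO-verified 7-day point prevalence abstinence at week 12, so early smoking does not settle it. Under 4.b and H1 a relapsed participant tries again on the assigned medication. Under F2 any new attempt is made without it. These are two different treatment policies, and the trial would be estimating the effect of whichever one staff happened to apply.

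The adherence outcome is also touched. C3 defines adherence as the proportion of expected medication taken as advised through week 12, and the advice itself is in dispute for these participants.

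**Working it through.** The plan gives no figure on this point to reproduce. The check compares the texts and then counts the treatment at stake.

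**1. The four rules side by side**

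| Section | Who | Instruction | Exception at 5 or more a day | Refers to F2 |
|---|---|---|---|---|
| F2 | Regular and heavy smokers, 5 or more a day | Stop | n/a | n/a |
| 2.g | Relapsed to regular smoking | Continue | None | No |
| 4.b | Smoking regularly | Continue, new quit date | None | No |
| H1 | Smoking regularly | Continue, new quit date | None | No |

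Regular smokers below 5 a day have one consistent instruction. The toxicity stop in 2.g has a different trigger and is not in conflict. The clash is confined to regular smokers at 5 or more a day.

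**2. The threshold.** Entry requires at least 5 cigarettes a day (2.a), and F2 applies from the same number. Section 3.b puts 5 to 9 a day in its lower patch-dose tier. F2 therefore does not single out unusually heavy smokers.

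**3. Treatment weeks given up if F2 is followed.** Inputs: 12 weeks of medication (3.b) and contacts at 1, 2 and 4 weeks after the quit date (E2).

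- Counted from the quit date: 12 − 1 = 11, 12 − 2 = 10, 12 − 4 = 8 weeks.
- If the 12 weeks include the pre-quit week, one fewer each: 10, 9 and 7 weeks.

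**4. The same loss as a share of scheduled post-quit dose** (3.b schedules)

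- *Patch, more than 9 a day* (daily mg × weeks): 21×8 + 14×2 + 7×2 = 210. Remaining: 189/210 = 90%, 168/210 = 80%, 126/210 = 60%.
- *Patch, 5 to 9 a day:* 14×8 + 7×4 = 140. Remaining: 126/140 = 90%, 112/140 = 80%, 84/140 = 60%.
- *Lozenge:* "Participants will then take 1 lozenge every 1-2 hours for 6 weeks, then 1 lozenge every 2-4 hours for 3 weeks", then every 4 to 8 hours for 3 weeks. Assuming equal waking hours, the relative rates are 4:2:1, so the total is 4×6 + 2×3 + 1×3 = 33. Remaining: 29/33 = 88%, 25/33 = 76%, 17/33 = 52%.
- *Varenicline, constant 2 mg a day:* 11/12 = 92%, 10/12 = 83%, 8/12 = 67%.

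Across products this is 88–92% at week 1, 76–83% at week 2 and 52–67% at week 4.

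**5. Sensitivity to timing and dose assumptions**

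- If the patch started in the pre-quit week, which 3.b does not state, both patch schedules give 89%, 78% and 56%.
- If varenicline's 12 weeks include the 7-day titration: 10/11 = 91%, 9/11 = 82%, 7/11 = 64%.
- Section 3.b encourages at least 4 lozenges a day. At the slow end of each interval, with 16 waking hours assumed, daily counts are 8, 4 and 2, the last raised to 4. The total is 8×6 + 4×3 + 4×3 = 72, and the shares become 64/72 = 89%, 56/72 = 78%, 40/72 = 56%.

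All of these are upper limits. F2 is advice, and participants receive their medication at visit 1 (3.i).

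**6. What cannot be calculated.** The documents give no distribution of cigarettes per day during treatment, so the number of participants under both rules is unknown.

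**The case against.** The strongest defence has three parts.

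*F2 may be a deliberate exception.* It covers smoking that is both regular and heavy, while the others cover regular smoking, and a specific rule can qualify a general one. This does not hold up well: the other three sections are unqualified, none refers to F2, and the threshold is the entry minimum. The F2 paragraph otherwise closely tracks 4.b and H1, which would fit a sentence left unrevised in one copy, though the document does not say so. Even if an exception was meant, staff working from 2.g, 4.b or H1 would not apply it.

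*The operative sections agree.* The sections on withdrawal, medical monitoring and safety monitoring all say continue, and the outlier sits in the statistical plan. The medication instructions (K9) and the counseling guide (K11) are listed but not supplied, and may state one rule. All of this is fair, and it limits how much confusion can be inferred. The protocol would still contradict itself.

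*The analysis is protected.* Much of this stands. Staff are blinded to assignment and genotype (2.d), and nothing suggests that either rule would be applied differently by arm or genotype. Participants who stop treatment and consent are still followed for smoking status (2.h), and dropouts count as smoking (F5). Although the 3.b statement on adherence analyses names only NRT and gives no method, other sections reach all products: F5 classifies the reason for stopping any study medication, C3 defines adherence for varenicline, patch and lozenge, and F3 lists adherence as a covariate. These provisions govern how outcomes and stopping are recorded and analysed. They do not decide which treatment is given.

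Continuous abstinence is little affected, since anyone smoking after the one-week grace period has already failed it.

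**Conclusion.** The contradiction is real and should be fixed. For participants smoking 5 or more cigarettes a day during treatment, F2 instructs the opposite of 2.g, 4.b and H1, and no supplied text resolves it.

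The problem concerns treatment received, not outcome collection. Following F2 at the week 1, 2 or 4 contact forgoes up to 11, 10 or 8 of the 12 weeks, if these run from the quit date and the advice is followed at once. No effect on abstinence is claimed, and neither the size nor the direction of any effect on the medication or interaction estimates can be derived from the documents. Confidence is high for the conflict in wording. Whether sites have a single working rule depends on K9 and K11.

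**What to change.** The investigator should choose one rule and state it in the same words in F2, 2.g, 4.b and H1.

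- **Default:** replace the F2 sentence with the 4.b and H1 rule, so that participants continue medication and set a new quit date as soon as possible. Leave the toxicity stop in 2.g unchanged.
- **Alternative:** if F2 is meant as a safety rule, give the reason and amend 2.g, 4.b and H1 to match.
- **Either way:** check that K9 and K11 carry the chosen rule.

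The cost is an amendment to one sentence (three if F2 is kept), the check of the two attachments, and a note to staff. Sample size, visits and analysis do not change. Anyone already told to stop stays in the assigned arm.

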### ***F3 Analysis Plan***

All analyses will first be conducted separately for European Ancestry (EA) and African American (AA) due to distinctly different allele frequencies and linkage disequilibrium across ancestry. If consistent genetic effects are seen across ancestry, samples of EA and AA ancestry will be combined in analyses with the covariate of race.

---

We will compare the abstinence outcome in the two placebo groups (placebo nicotine patch plus placebo nicotine lozenge vs. placebo varenicline pill). If they are comparable which is consistent with prior experience of other placebo-controlled smoking cessation trials, they will be pooled for further analyses.

The primary outcome is CO-confirmed point prevalent abstinence at end of treatment (12 weeks), defined if subjects deny smoking during 7 days prior of the end of treatment and provide a breath sample with CO <8 ppm.

Hypothesis #1 is to examine whether medication effect (cNRT vs. placebo) varies with CHRNA5 (i.e. a genotype X medication interaction). A series of generalized linear models will be used to examine main effects of genotype (rs16969968) and medication before testing genotype x medication interactions, with sex, age, and study cohort as covariates using logistic regression models.

Hypothesis #2 is to examine whether medication effect (varenicline vs. placebo) varies with CHRNA5 (i.e. a genotype X medication interaction). A series of generalized regression models will be used to examine main effects of genotype (rs16969968) and medication before testing genotype x medication interactions, with sex, age, and study cohort as covariates using logistic regression models.

#### Analysis Plan.

We will use generalized linear models with logit as the link function to model the primary outcome (7-day point prevalence abstinence at 12 weeks/end of treatment). We will construct contrast models for each specific hypothesis testing and compare the goodness of fit for each contract. The primary method of analysis will be estimating a standard series of regression equations to test main effects, and gene – environment interaction (effect moderation).

Our primary analyses will focus on SNPs, rs16969968, tagging nicotinic receptor genes *CHRNA5-A3-B4* and medication in our hypotheses testing for gene-medication interactions. Additional covariates include age, gender, measures of nicotine dependence severity (such as pre-quit cigarettes smoked per day), adherence, and non-genetic factors.

Secondary cessation outcomes include CO-confirmed 3-month continuous abstinence with a 1-week grace period, 7-day abstinence at 6 months, and 1 year, time to relapse (using Cox regression models), and withdrawal severity. Generalized Estimation Equation (GEE) will be used in longitudinal models comprising abstinence outcomes across 3 months, 6 months, and 1 year in secondary analyses.

Detailed analysis plan is included in the Statistical Analysis Plan (SAP) in Appendix K10.

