### A2 Primary Hypothesis

Hypothesis #1 is to examine whether medication effect (cNRT vs. placebo) varies with CHRNA5 (i.e. a genotype X medication interaction). A series of logistic regression models will be used to examine main effects of genotype (rs16969968) and medication before testing genotype x medication interactions, with sex, age, and study cohort as covariates using logistic regression models.

Hypothesis #2 is to examine whether medication effect (varenicline vs. placebo) varies with CHRNA5 (i.e. a genotype X medication interaction). A series of logistic regression models will be used to examine main effects of genotype (rs16969968) and medication before testing genotype x medication interactions, with sex, age, and study cohort as covariates using logistic regression models.

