### **C3 Rationale for the Selection of Outcome Measures**

We will conduct a randomized controlled smoking cessation trial of 822 participants to examine the association between the genetic variants (CHRNA5), treatment, and cessation success (abstinence at end of treatment (ABST\_EOT)). We will evaluate secondary cessation outcomes (abstinence at 6 months and 1 year).

**Primary Outcome Measure:** 7-day point prevalence abstinence [Time Frame: Week 12]  
The definition of this measure requires: (a) no self-reported smoking (not even a puff of a cigarette) for at least the 7 days prior to the assessment, and (b) CO biochemical verification of abstinence.

**Secondary Outcome Measures:** Continuous Abstinence (11 weeks) [Time Frame: 12 weeks with the first 1 week initial grace period]

The definition of this measure requires: Not taking even 1 cigarette puff from target quit date to end of treatment with the first 1 week initial grace period.

**7-day point prevalence quit rate** [Time Frame: Week 24]

The definition of this measure requires: (a) no self-reported smoking (not even a puff of a cigarette) for at least the 7 days prior to the assessment, and (b) biochemical verification of abstinence.

Number of days to lapse and relapse [Time Frame: Assessed from the target quit day through 52 weeks.]

The number of days to lapse is defined as the number of days from the target quit date until the participant reports smoking (even a single puff). The number of days to relapse is defined as the number of days from the target quit day until the first of seven consecutive days of smoking.

Initial Cessation [Time Frame: Assessed for the first seven days after the target quit date.]  
Defined as at least 1 day of abstinence during the first 7 days after the target quit day.

Longitudinal models of abstinence outcomes across multiple time points [ Time Frame: 0-52 Weeks ]

The definition of this measure requires; no self-reported smoking (not even a puff of a cigarette) for at least 7 days prior to the assessment.

Longitudinal models of smoking quantity in cigarettes per day outcomes across multiple time points. [ Time Frame: 0-52 Weeks ]The definition of this measure requires self-reported cigarettes per day.

Medication adherence [ Time Frame: Pre-quit week to Week 12 ]Adherence is the proportion of expected medication (varenicline, patch, lozenge) taken as advised during pre-quit week to week 12

Side effects [ Time Frame: Pre-quit week to Week 12 ]

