## ***F5 Missing Outcome Data***

If a participant prematurely discontinues the study medication, the reason for discontinuation will be determined and classified as primarily due to an adverse event, or lack of efficacy, not wanting to take another medication, or others. We will examine missing data for causes and compare the groups with respect to side effects and efficacy. We will adhere to the intent-to-treat principle for smoking outcome analyses, so that dropouts will be treated as smoking. In addition, we will analyze the missing data under conditions of both missing completely at random (MCAR) and missing at random (MAR), and use appropriate strategies such as imputation when appropriate.

Participants who drop off the trial before they get a dose of the study medication/placebo will be included in the analyses of efficacy if they receive the medication packet. They will be included in the safety analyses if medication was dispensed to them. We will ensure an appropriate informed consent process to minimize the probability of drop out. We will also assess level of adherence to the study protocol and these information will be available for use in secondary analyses.

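### Section F3 lists adherence, measured after randomisation, among the primary-model covariates and conflicts with the covariate set given for Hypotheses 1 and 2

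*Combined protocol and SAP*

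**What the plan says.** The Analysis Plan part of F3 first describes the logit model for week-12 abstinence and the primary method of analysis. It continues: "Our primary analyses will focus on SNPs, rs16969968", together with medication, for the gene-by-medication tests. The next sentence reads: "Additional covariates include age, gender, measures of nicotine dependence severity (such as pre-quit cigarettes smoked per day), adherence, and non-genetic factors". Secondary outcomes start only in the following paragraph, and nothing confines the list to secondary or sensitivity models.

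Other sections bear on this:

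- A2 and the hypothesis statements in F3 specify the interaction models for both hypotheses "with sex, age, and study cohort as covariates using logistic regression models". F3 adds race if the ancestry groups are pooled: "samples of EA and AA ancestry will be combined in analyses with the covariate of race".
- C3 lists adherence as a secondary outcome: "Adherence is the proportion of expected medication (varenicline, patch, lozenge) taken as advised during pre-quit week to week 12".
- Section D3, 3.b, places randomisation before that window: "During the baseline visit (visit 1), all participants will be randomized at 1:1:1". It also says: "Dose changes or discontinuation of NRT may be recommended; all changes will be addressed in analyses of adherence outcomes".
- F5 states: "We will adhere to the intent-to-treat principle for smoking outcome analyses, so that dropouts will be treated as smoking". It then makes adherence information available for secondary analyses.
- F3 and F4 refer to Appendix K10 for the detailed analysis plan. K10 is listed among the attachments, but its text was not available for this review.

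**The concern.** A covariate in the primary model of a randomised trial should be fixed before assignment. Adherence is not. It can respond to the drug, through side effects and the dose changes or discontinuations that 3.b foresees, and it shares causes with quitting, such as motivation. Conditioning on it compares people who are alike in adherence but no longer alike in those causes. The randomised comparison is then lost, and the bias can go either way.

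Two results are exposed. The medication main effect, which A1, C1 and D1 say will be tested, would no longer be the effect of assignment. The genotype-by-medication interaction, which is the test for Hypotheses 1 and 2, would be distorted if adherence varies by genotype and medication jointly.

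There is also a problem of pre-specification. With two different covariate lists for the primary model, the choice between them could be made after the data are seen.

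**Working it through.** **The text, side by side**

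| Place | Covariates for the primary models |
|---|---|
| A2, and F3 hypothesis statements | sex, age, study cohort |
| F3, if ancestry groups are pooled | race added |
| F3, Analysis Plan part | age, gender, dependence severity, adherence, non-genetic factors |

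The last list omits study cohort, adds a variable that does not exist at randomisation, and ends with an undefined class. The plan gives no figure to reproduce on this point; the power statement in F1 names no covariates.

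**Size, by simulation**

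From the documents: 822 / 3 = 274 per arm, and placebo abstinence of 20% (F1). Everything else is assumed.

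- Genotype G ~ Binomial(2, 0.35), centred as Gc. A = 1 for active, 0 for placebo. U and e are independent standard normal; U is an unmeasured trait such as motivation.
- Adherence proportion: H = expit(0.3 + aA·A + u·U + aAG·A·Gc + e).
- Logit of abstinence: b0 + u·U + bA·A + bAG·A·Gc + bAH·A·(H − 0.55), with b0 = −1.386, −1.45, −1.6 for u = 0, 0.4, 0.8. This gives placebo abstinence of 19–20%.
- Logistic models on A and Gc (plus A·Gc for the interaction) are fitted with and without H. Odds ratios use 200,000 per arm; rejection rates use 4,000 trials of 274 per arm.

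*Medication odds ratio, drug truly null (bA = bAG = bAH = aAG = 0, aA = −0.7 or +0.7)*

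| u | Mean adherence, active vs placebo | OR without H | OR with H | False-positive rate, without to with H |
|---|---|---|---|---|
| 0 | lower in active | 1.00 | 1.00 | – |
| 0.4 | 42% vs 56% | 1.00 | 1.10 | 4.4% to 6.7% |
| 0.4 | 69% vs 56% | 1.00 | 0.91 | – |
| 0.8 | 42% vs 56% | 1.00 | 1.29 | 4.9% to 20.9% |
| 0.8 | 68% vs 56% | 1.00 | 0.79 | – |

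Because the true odds ratio is 1, these shifts cannot be the ordinary change in an odds ratio when a predictor is added to a logistic model. They are bias.

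*Interaction odds ratio (u = 0.8, aA = −0.3, bA = 0.6)*

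| Case | Without H | With H | Rejection rate, without to with H |
|---|---|---|---|
| Adherence unrelated to genotype × medication (bAG = ln 2, aAG = bAH = 0) | 1.84 | 1.89 | – |
| aAG = 0.3, bAG = 0.55, bAH = 1.5 | 1.68 | 1.51 | 43% to 28% |
| aAG = 0.6, bAG = 0.55, bAH = 1.5 | 1.81 | 1.40 | 52% to 20% |
| Null interaction (bAG = bAH = 0, aAG = 0.6) | 1.00 | 0.80 | 5.2% to 10.0% |

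In the active arm, aAG = 0.3 corresponds to adherence of about 46% vs 57% between the two homozygous groups, and aAG = 0.6 to about 42% vs 64%. At u = 0 the null interaction does not move. An allele frequency of 0.20 gives similar results (1.72 to 1.55 and 1.83 to 1.43).

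A second model, with adherence on an unbounded scale, allele frequency 0.30 and 400,000 participants, moves the same way: null medication effect 1.00 to 1.20, null interaction 1.00 to 0.82, true interaction 1.79 to 1.49.

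**The case against.** The best defence is that the sentence speaks of additional covariates and does not say that they enter the models for Hypotheses 1 and 2. Those models are specified by name in A2 and F3, and C3, 3.b and F5 all give adherence a secondary role. On that reading the list is a menu for further models, one word is misplaced, and K10 may already put it right.

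That shows what was probably intended, but F3 does not say it. The list follows directly on the primary analyses and repeats age and gender, which would be redundant if it only supplemented the other set. Even as a supplement to that set, it would put adherence in the primary model.

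Three parts of the objection stand:

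- The largest figures concern the medication main effect under a strong assumed confounder. The primary tests are interactions, and these move materially only if adherence differs by genotype and medication. The documents do not say whether it does, and the largest interaction shifts need a gap of about 22 points between homozygous groups.
- The intent-to-treat statement in F5 concerns who is analysed and how dropouts are counted; a covariate does not by itself breach that. The main objection is to the estimand. There is still a practical clash: adherence is reported at follow-up contacts, so dropouts counted as smoking may lack the covariate and fall out of a complete-case fit.
- Dependence severity measured at baseline is a legitimate covariate. The difficulty is only timing: the E2 schedule also labels Visit 2, after randomisation, as pre-quit.

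**Conclusion.** The concern holds. As written, F3 places a post-randomisation variable among the primary-model covariates and contradicts the covariate set in A2 and F3 and the role F5 gives to adherence. This must be corrected before analysis because it defines the model for the primary test.

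The size of the harm is conditional. It is zero for a null medication effect if adherence and quitting share no unmeasured cause. Under the assumed confounding, a null medication odds ratio becomes roughly 0.79 to 1.29. The interaction is almost unaffected unless adherence depends jointly on genotype and medication; in the cases tried where it does, a true interaction shrinks and a null one can appear as 0.80. These figures illustrate direction and plausible scale and do not estimate what would happen in this trial. The textual conflict does not depend on them. Whether K10 resolves it could not be checked.

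The timing of cigarettes per day and the undefined non-genetic factors are minor drafting points; the conclusion does not rest on them.

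**What to change.** Replace the covariate sentence in F3 with something like:

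> The primary models for Hypotheses 1 and 2 adjust for sex, age and study cohort, and for race where ancestry groups are combined. No variable measured after randomisation enters a primary model. Adherence is analysed as a secondary outcome and in analyses labelled secondary.

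If cigarettes per day is kept in any model, define it as the Visit 1 value collected before medication is dispensed. Name the non-genetic factors or delete the term. Use the same wording in Appendix K10.

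The cost is one sentence in F3 and the matching text in K10. Data collection, sample size and budget are unaffected.
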